5.0 STATISTICAL METHODS

5.1 General Data Handling

Descriptive statistics on continuous variables will include mean, standard deviation, median, and range. Confidence intervals will be included for selected endpoints. Categorical variables will be summarized using frequency counts and percentages. A confidence level of 95% will be used for the confidence intervals. Statistical testing will be two-sided with a significance level of 0.05 or one-sided with a significance level of 0.025 unless specified otherwise. Data listings of individual subject data may be provided.

The baseline values are those that are obtained at the closest visit prior to the surgery. The arithmetic difference between the baseline and the postoperative visit are defined as follows:

Change from baseline = postoperative value – baseline value

Percent change from baseline = change from baseline ÷ baseline X 100.

The Safety Population includes all subjects for whom a Hydrus microstent was implanted or implantation was attempted.

5.2 Study Populations

The **Effectiveness Population** will consist of all the subjects who undergo the Hydrus implantation surgery and are not discontinued early from the study due to unrelated reasons such as death or relocation. The primary analyses on the primary and secondary effectiveness endpoints will be based on the **Effectiveness Population**. The reasons for discontinuation will be reported.

Intent to Treat. The ITT population will include all subjects undergoing Hydrus Microstent implantation surgery. For this study the ITT population is the safety population.

Per Protocol. The Per Protocol (PP) population will include all implanted subjects who meet the following criteria:

- Subject meets all protocol eligibility criteria.
- Subject completes the 12-month visit.
- Subject received secondary surgical intervention (SSI) for controlling IOP will be included and treated as non-responder
- Subjects without adverse events that lower IOP such as cyclodialysis cleft.
- Additional criteria, if any, will be established before the data review and database closure.

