5.3 Effectiveness Endpoints Analyses

5.3.1 Primary Effectiveness Endpoint

The primary effectiveness outcomes for this study is:

- Proportion of subjects with $\geq 20\%$ decrease in mean diurnal IOP at 12 months while maintaining the same or fewer number of medications as at baseline

The primary analyses of the primary endpoint will be based on the Effectiveness Population. The exact 95% confidence interval of the response rate will be calculated based on binomial distribution.

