6.1.3 Unanticipated Adverse Device Effects

An unanticipated adverse device effect (UADE) is any serious adverse effect on health or safety or any life-threatening problem or death caused by or associated with a device, if that effect, problem, or death was not previously identified in nature, severity or degree of incidence in the investigational plan or application (including a supplementary plan or application). UADEs also include any unanticipated sight-threatening events and any other unanticipated serious problem associated with a device that relates to the rights, safety, or welfare of subjects.

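### The primary analysis set can drop an eye that has already had surgery to control IOP, and this can raise the reported response rate

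*Combined protocol and SAP*

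**What the plan says.** Section 5.2 (Study Populations) defines the Effectiveness Population as subjects who undergo the implantation surgery and "are not discontinued early from the study due to unrelated reasons such as death or relocation". It adds that the reasons for discontinuation will be reported. Section 5.3.1 states: "The primary analyses of the primary endpoint will be based on the Effectiveness Population". Section 5.2 assigns the secondary endpoint to the same set.

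The primary endpoint is the proportion of subjects with at least a 20% "decrease in mean diurnal IOP at 12 months while maintaining the same or fewer number of medications as at baseline", with an exact binomial 95% confidence interval. No failure event before month 12 is part of that definition.

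Section 5.2 defines two other sets:

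- **ITT.** "The ITT population will include all subjects undergoing Hydrus Microstent implantation surgery". It is equated with the Safety Population, which under 5.1 includes attempted implantations. Sections 5.2 to 5.3.3 assign no effectiveness analysis to it.
- **Per Protocol.** One criterion reads "Subject completes the 12-month visit"; the next reads "Subject received secondary surgical intervention (SSI) for controlling IOP will be included and treated as non-responder".

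The documents give no sample size, target rate, performance goal, expected dropout, missing-data rule or sensitivity analysis for the primary endpoint.

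**The concern.** Membership of the primary set depends on an event after surgery, and the text makes no exception for an eye whose outcome is already settled. Take a subject who has IOP-lowering surgery at month 4 and relocates at month 8. The plan itself regards such surgery as non-response, but says so only for Per Protocol. Read as written, the Effectiveness Population loses this subject at month 8.

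The sequence is plausible. Section 3.2 enrols refractory glaucoma, and section 6.8.1 lists surgical re-intervention in the study eye as an anticipated event.

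No control group or performance goal is described, so the response rate and its interval are the effectiveness result. A rule that can remove non-responders from the denominator acts directly on that result. Neither the meaning of unrelated nor the person who judges it is stated, and the list of reasons is open-ended.

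**Working it through.** The plan states no figure that could be reproduced, so the check has two parts: what the text does with the example subject, and what removal does to the rate.

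**1. The subject with SSI at month 4 who relocates at month 8**

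| Set (5.2) | Is the subject counted as a non-responder? |
|---|---|
| Effectiveness Population | No. Relocation is a named reason for removal, with no exception for SSI |
| Per Protocol | Unclear. The SSI criterion includes the subject; the 12-month completion criterion does not |
| ITT | The subject is a member, but no effectiveness analysis uses this set |

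**2. Effect on the observed rate**

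Let *x* be the responders, *n* the denominator with known failures kept, and *k* the known failures removed. Then *x*/(*n* − *k*) > *x*/*n* whenever *x* > 0 and *k* > 0.

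Illustration, all inputs assumed: 40 implanted, 20 responders, 6 exits labelled unrelated, 3 of these after SSI. Intervals are Clopper-Pearson, 95%.

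| Handling | Rate | Exact 95% CI |
|---|---|---|
| As planned, all 6 removed (40 − 6 = 34) | 20/34 = 58.8% | 40.7 to 75.4 |
| The 3 with SSI kept as non-responders (34 + 3 = 37) | 20/37 = 54.1% | 36.9 to 70.5 |
| All 6 counted as non-responders | 20/40 = 50.0% | 33.8 to 66.2 |

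The effect of the SSI gap is the difference between the first two rows: 58.82 − 54.05 = 4.8 points.

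Range, also on assumed inputs: with 30 to 100 subjects, response rates of 40 to 70% and about 3 to 10% removed, and with *every* removed subject a known failure, the rate rises by 1.2 points (40/97 against 40/100) to 7.8 points (42/54 against 42/60).

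**3. Effect against the true rate**

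Let *f* be the share of operated eyes removed. The bias of removal is *f* × (*p* retained − *p* excluded). With *f* = 10% and *p* retained = 60%:

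| Response rate among excluded eyes | Bias, points |
|---|---|
| 0% (all failed) | 0.10 × (60 − 0) = +6.0 |
| 30% | 0.10 × (60 − 30) = +3.0 |
| 60% (exit independent of outcome) | 0 |
| 70% | 0.10 × (60 − 70) = −1.0 |

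**4. Effect of the remedies if exit is independent of outcome**

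Take *f* = 10%, *p* = 60%, and 20% of exits already failed. Keeping only those failures gives 0.90 × 0.60 / (0.90 + 0.10 × 0.20) = 0.54/0.92 = 58.7%. Counting every exit as non-response gives 0.90 × 0.60 = 54.0%. Both lie below the true 60%.

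**The case against.** The strongest reply is that removal for truly unrelated reasons is unbiased. A reader might infer that the response rate is inflated, or that the error always runs upward. The documents do not support either. The direction is certain only relative to counting the removed subjects as non-responders. Against the true rate the bias can be zero or slightly negative, as step 3 shows. This part of the reply stands in full.

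Three further inferences should also be resisted:

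- **That Per Protocol certainly loses the subject.** The SSI criterion can be read as overriding the completion criterion. The text is ambiguous.
- **That device-associated deaths would be removed as unrelated.** Section 6.1.3 covers "any life-threatening problem or death caused by or associated with a device", but it is a general definition. The natural reading of 5.2 is deaths that are unrelated, and 6.5 already provides a relatedness assessment. The two sections are simply not linked.
- **That exits are classified with knowledge of the outcome.** The documents do not say who classifies them or when. Both named examples, death and relocation, are objective events.

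It is also fair that the primary endpoint has no failure status before month 12, that reasons for discontinuation will be reported, and that a shift of 4.8 points is small beside an exact interval more than 30 points wide.

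This does not remove the point. The plan itself treats SSI as non-response but does not carry that rule into the set that bears the primary result. Reporting the reasons shows the exits without putting a failed eye back into the estimate.

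**Conclusion.** The point holds as a possibility built into a stated rule, not as a demonstrated inflation. Followed exactly, section 5.2 can remove from the primary denominator an eye that has already had surgery for IOP, and no other analysis in the plan is sure to show it as a non-responder. This can raise the response rate.

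The size is unknown, because the documents give neither a sample size nor an exit rate, nor how often SSI precedes an unrelated exit. The 4.8-point illustration and the range of 1.2 to 7.8 points rest wholly on assumed inputs, and that range further assumes that every removed subject had failed. No pass or fail decision is shown to turn on it, since no performance goal is stated. The change is worth making because it is cheap and applies a rule the plan already contains.

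**What to change.** **Section 5.2.** Add to the Effectiveness Population definition:

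- *A subject who has SSI for IOP before discontinuation stays in the Effectiveness Population as a non-responder, whatever the reason for leaving.*
- *Unrelated means assessed as not related to the device or procedure under section 6.5.* Section 6.5 is written for adverse events, so say that the same question is answered for exits such as relocation.

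**Section 5.3.1.** Beside the primary result, report the response rate and exact 95% CI on the ITT population already defined, with a missing 12-month diurnal IOP counted as non-response. Label this a conservative bound; multiple imputation may be added. Show subjects with attempted but unsuccessful implantation separately. They belong to ITT, but under footnote 6 of the Schedule of Visits (section 4.0) they may be followed for only 1 month, so their missing 12-month value does not mean the same as an early exit.

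**Cost.** A few sentences and one table, with no new subjects or assessments. The reported rate may be slightly lower. Keeping known failures while removing other unrelated exits is asymmetric and can bias the rate slightly down (58.7% against 60% in step 4). The ITT row makes the handling of exits visible.

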3.2 Screening Inclusion Criteria

Subjects must meet the following inclusion criteria to be eligible. Unless otherwise specified, all ocular criteria refer to the study eye only.

- Male and female patients at least 45 years of age
- A diagnosis of open-angle glaucoma (POAG, PXG, or PG), with optic nerve pathology described by one or more of the following:
 - Diffuse thinning, focal narrowing, or notching of the optic disc rim, especially at the inferior or superior poles with or without disc hemorrhage;
 - Localized abnormalities of the peripapillary retinal nerve fiber layer, especially at the inferior or superior poles; or
 - Optic disc neural rim asymmetry of the two eyes consistent with loss of neural tissue
- BCVA of 20/80 or better in the study eye
- Subject has refractory glaucoma, defined as:
 - Previously failed filtering or cilioablation procedure (i.e., includes incisional glaucoma surgery, cryotherapy, and cyclodiode therapy) and with uncontrolled IOP on medical therapy

or

- IOP is uncontrolled on maximum tolerable medical therapy (e.g., a minimum of four or more classes of topical glaucoma medications, or fewer if others are not tolerated or are not effective)
- Subject has been on current glaucoma medication regimen for at least 30 days
- A medicated IOP of ≥ 20 mmHg and ≤ 35 mmHg by Goldmann applanation tonometry
- Open anterior chamber angle anatomy (e.g., no peripheral anterior synechiae or iris processes) visualized by gonioscopy with a Shaffer angle grade of \geq III in all four quadrants
- Visual field examination using Humphrey-Zeiss 24-2 SITA Std., with mean deviation (MD) of -3 dB or worse (conducted within 60 days of Screening is acceptable)
- Visual field defects consistent with glaucomatous optic nerve damage, and with at least one of the following two findings:
 - A cluster of 3 or more points in an expected location of the visual field depressed below the 5% level, at least 1 of which is depressed below the 1% level on pattern deviation (PD) plot
 - Glaucoma hemi-field test “outside normal limits”
- The subject is able to understand the requirements of the study and provide written informed consent
- Subject is willing to follow study instructions, agrees to comply with all study procedures and attend all scheduled follow-up exams for 12 months postoperatively

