3.3 Screening Exclusion Criteria

Excluded from the study will be individuals with the following characteristics. Unless specified otherwise, all ocular criteria refer to the study eye only.

- Secondary glaucoma other than pseudoexfoliative and pigmentary (e.g., neovascular, uveitic, traumatic, steroid induced, lens induced, or glaucoma associated with increased episcleral venous pressure)
- Diagnosis of acute angle closure, chronic angle closure, or congenital, malignant, or developmental glaucoma
- Central visual field depression within 5 degrees of fixation with sensitivity < 15 dB in both hemifields on the numerical/dB plot
- Pre-perimetric glaucoma
- Ocular hypertension
- Shallow or flat anterior chamber
- Presence of peripheral anterior synechiae or iris processes obscuring angle visualization
- Central corneal thickness greater than 620 or less than 480 microns
- History of complicated intraocular surgery (e.g., vitreous in anterior chamber, zonular dehiscence)
- History of failed Schlemm's canal procedure (including but not limited to Glaukos iStent, Ellex ABiC, SightSciences Trab360, or New World Medical Kahook Dual Blade)
- Epithelial or fibrous downgrowth

- Aphakia
- Currently implanted anterior chamber IOL
- Retinal laser within 90 days prior to screening
- A need for additional ocular surgery (e.g., cataract surgery) or retinal laser procedure within the 12-month postoperative period
- Proliferative diabetic retinopathy (PDR)
- History of retinal detachment repair with silicone oil or scleral buckling procedure
- Corneal dystrophy (e.g., Fuch's Dystrophy, defined as > 12 confluent endothelial guttae) or corneal opacity
- Previous corneal surgery, including lamellar or penetrating keratoplasty, LASIK or PRK
- Fellow eye best-corrected visual acuity (BCVA) worse than 20/200
- Inability to complete a reliable Humphrey-Zeiss 24-2 SITA Std visual field on the study eye (fixation losses, false positive, and false negative errors should not be greater than 33%)
- Fellow eye visual field mean deviation worse than -18.00 dB
- Exudative age-related macular degeneration (AMD)
- History of intraocular inflammation or infection within 90 days prior to screening
- Use of oral hypotensive medication (e.g., acetazolamide) for glaucoma treatment
- Uncontrolled systemic disease that in the opinion of the Investigator would put the subject's health at risk and/or prevent the subject from completing all study visits

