5.3.2 Secondary Effectiveness Endpoint

The secondary effectiveness endpoint for this study is:

- Mean reduction in diurnal IOP at 12 months.

The change in diurnal IOP from baseline at 12 months will be calculated for each subject, and the mean change in diurnal IOP and the corresponding 95% confidence interval will be calculated.

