Events occurring secondary to other events should be recorded as sequelae to the primary cause; a "primary" event, if clearly identifiable, should represent the most accurate clinical term to record as the AE. Treatment for an adverse event should not be recorded as the adverse event. Instead, the reason for the treatment or procedure should be assessed as the potential adverse event.

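### The rule that further IOP-lowering surgery means non-response sits only in the Per Protocol criteria, so as written the primary analysis can count such an eye as a Hydrus responder

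*Combined protocol and SAP*

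**What the plan says.** Section 5.2 defines the analysis sets. The Per Protocol list includes the bullet "Subject received secondary surgical intervention (SSI) for controlling IOP will be included and treated as non-responder". No other sentence in the documents links re-operation to responder status.

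The Effectiveness Population, in the same section, takes everyone who has the implantation surgery, provided they "are not discontinued early from the study due to unrelated reasons such as death or relocation". The ITT population is all subjects undergoing implantation surgery. Neither definition mentions SSI.

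Section 5.3.1 defines response as a fall of at least 20%, specifically a "decrease in mean diurnal IOP at 12 months while maintaining the same or fewer number of medications as at baseline". It then says: "The primary analyses of the primary endpoint will be based on the Effectiveness Population". The result is reported as a proportion with an exact binomial 95% confidence interval. No hypothesis or performance goal is given. Section 5.3 assigns no analysis to the Per Protocol set.

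Section 5.3.2, on the secondary endpoint, says "The change in diurnal IOP from baseline at 12 months will be calculated for each subject" and is also silent on SSI.

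**The concern.** The study has a single arm, so the 12-month response rate is its main effectiveness result. A pressure reduction achieved with a later operation is not evidence that the microstent worked. The plan accepts this in its Per Protocol rule but does not carry the rule into the analysis it calls primary. A programmer following 5.3.1 to the letter would credit the effect of the second operation to Hydrus.

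SSI is foreseeable in this population. Section 3.2 requires refractory glaucoma. One route is uncontrolled pressure on medication after a failed filtering or cilioablation procedure; the other is that "IOP is uncontrolled on maximum tolerable medical therapy". The number of cases should be limited by the exclusion in 3.3 of eyes with "A need for additional ocular surgery (e.g., cataract surgery) or retinal laser procedure within the 12-month postoperative period". That is a screening judgement, however, and does not say how to score an eye that has surgery after all.

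**Working it through.** **Step 1: follow one eye through the text.** Take an eye that receives Hydrus, later has surgery to control IOP, stays in follow-up, and at 12 months has a mean diurnal IOP at least 20% below baseline on no more medications than at baseline.

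| Question | Effectiveness Population (primary) | Per Protocol set |
|---|---|---|
| Is the eye included? | Yes. It was not discontinued early for an unrelated reason (5.2) | Yes, if it meets the other Per Protocol criteria (5.2) |
| Is there an SSI rule? | None in 5.2 or 5.3.1 | Yes, the Per Protocol bullet in 5.2 |
| How is it scored? | Responder, since both conditions in 5.3.1 are met | Non-responder |

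The same eye with the same data is scored in opposite ways. Sections 5.3.2 and 5.3.3 add no SSI rule. Sections 6.7 and 6.8.1 mention surgery only as an action taken and as an anticipated adverse event.

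**Step 2: direction and size.** Let *s* be the share of eyes with SSI for IOP control and *q* the share of those eyes that meet the IOP and medication conditions. The denominator is the same under both scorings, so

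rate as written − rate with SSI as non-response = *s* × *q* ≥ 0.

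The plan states no figure that could be reproduced: no sample size, expected response rate, SSI rate or qualifying share. The values below are all assumptions.

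- *s* = 0: 0 points
- *s* = 5%: 0.05 × 0.5 = 2.5 points; 0.05 × 1 = 5 points
- *s* = 10%: 0.10 × 0.5 = 5 points; 0.10 × 1 = 10 points

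**Step 3: effect on the reported interval.** The exact (Clopper-Pearson) 95% limits for *x* responders of *n* are the 0.025 quantile of Beta(*x*, *n* − *x* + 1) and the 0.975 quantile of Beta(*x* + 1, *n* − *x*). Assume 45% of all eyes are responders without SSI.

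| Assumed n | Assumed qualifying SSI eyes | SSI as non-response | As written |
|---|---|---|---|
| 60 | 3 (10% SSI with half qualifying, or 5% with all) | 27/60 = 45.0% (32.1 to 58.4) | 30/60 = 50.0% (36.8 to 63.2) |
| 60 | 6 (10% SSI, all qualifying) | 27/60 = 45.0% (32.1 to 58.4) | 33/60 = 55.0% (41.6 to 67.9) |
| 40 | 4 (10% SSI, all qualifying) | 18/40 = 45.0% (29.3 to 61.5) | 22/40 = 55.0% (38.5 to 70.7) |
| 100 | 10 (10% SSI, all qualifying) | 45/100 = 45.0% (35.0 to 55.3) | 55/100 = 55.0% (44.7 to 65.0) |

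For given *s* and *q* the shift is the same at every sample size. A larger study narrows the interval but does not remove the bias.

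**The case against.** The best counter-argument is that the rule is misplaced rather than limited. It tells the analyst how to code a response, which is an odd thing to find in a list of population criteria. Since 5.3 assigns no analysis to the Per Protocol set, a rule confined to that set would govern no specified analysis. The sponsor may well have meant it as a general convention. No sentence states outright that an SSI eye is a responder; that follows only from literal application of 5.3.1. All of this is fair, and intent cannot be settled from the text. But nothing extends the rule, and the primary analysis will be programmed from 5.3.1. If the rule was meant generally, saying so changes nothing the sponsor intended. If the sponsor meant the primary analysis to count outcomes regardless of later surgery, the plan neither says nor justifies that.

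The size is also open to challenge. Every numerical input is assumed, the 10-point figure needs all SSI eyes to qualify, and the effect is zero if no SSI occurs. The re-intervention item in 6.8.1 covers re-operation in general, so it does not by itself show that surgery for IOP is expected; the entry criteria in 3.2 are the better support. These points limit the claim about size. They do not affect the inconsistency or its direction.

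Finally, SSI is not defined in section 7.0 or elsewhere, and the existing bullet has no time limit. Copying it unchanged would leave some scoring decisions open. That stands, and the fix allows for it.

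**Conclusion.** The point holds. As written, 5.3.1 scores as a responder an eye that qualifies after further IOP-lowering surgery, contrary to the plan's only statement on SSI. The resulting error in the primary response rate is zero or upward. It is 2.5 to 10 percentage points if 5% to 10% of eyes have SSI and half to all of those qualify, and nil if there is no SSI. Those rates are assumptions; the documents support the direction but not a particular size. With no performance goal stated, the consequence is an overstated rate and interval, not a changed pass/fail decision. It should be fixed: it concerns the scoring of the primary endpoint, the bias is in the favourable direction only, and the remedy is cheap.

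**What to change.** Add one sentence to 5.3.1: a subject with an SSI for controlling IOP in the study eye before the 12-month assessment is a non-responder for the primary endpoint, in the Effectiveness Population and in every other analysis set. The non-responder scoring is the plan's own rule. The time limit is new and should be identified as an addition. State in section 7.0 which procedures count as SSI for this purpose; that list is for the sponsor to set.

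As a minor clarification, 5.3.2 should say whether the mean change uses the observed 12-month IOP regardless of SSI. Its present wording is not an error in itself.

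The cost is small. No subject is removed and the denominator is unchanged. The reported response rate may be lower. Each re-intervention must be classified as for IOP control or not. Most of the inputs are already collected: surgical intervention is a recorded action (6.7), surgical re-intervention in the study eye is a listed event (6.8.1), and under 6.2 "the reason for the treatment or procedure should be assessed as the potential adverse event". Because that section directs sites to record the underlying reason and not the treatment as the event, a specific case report form item for surgery to control IOP may be needed to make the classification reliable.
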